Investigational plan

Protocol Title: Safety and efficacy of a contained electromechanical power morcellation systems for laparoscopic hysterectomy and myomectomy.

NCT#: NCT02777203

Date: 4/11/2017

Protocol Number: Pending. The study sponsor will be the Advanced Gynecologic Surgery Institute. The investigational site will be ALGH. The study will be reviewed by the Advocate Health Care Institutional Review Board (IRB) per appropriate protocol.

Objectives

The purpose of this feasibility study is to determine the safety and efficacy of using an insufflated bag for electromechanical power morcellation during laparoscopic hysterectomy and myomectomy for tissue removal. Our goal is to prove that the integrity of the bags is maintained throughout and after insufflation and power morcellation.

The hypothesis is that the bag will remain integral and there is will be no leakage from the bag during and after power morcellation using the described contained system, confirming the safety and efficacy of the systems.

Inclusion and Exclusion Criteria

Inclusion criteria will be adult premenopausal women (equal or greater than 18 years old) at ALGH without symptoms of menopause undergoing robotic or laparoscopic total or supracervical hysterectomies or myomectomies for the indication of symptomatic uterine fibroids who are not candidates for specimen removal via mini-laparotomy incision (as deemed by the study surgeon) or who have refused mini-laparotomy and therefore require power morcellation for tissue removal.

Exclusion criteria include known or suspected malignancy, peri- or post-menopausal women diagnosed with uterine fibroids, specimen that can be removed without power morcellation (e.g., vaginally or through laparoscopic trocars), and adults unable to consent.

These patients will be screened and consented pre-operatively. The final decision on a patient's inclusion or exclusion from the study will occur intra-operatively after evaluation of the size and characteristics of the uterus.

Study-Wide Number of Subjects

As this will be a feasibility study, a maximum of 110 patients will be enrolled into the study. Over a one year time, the investigation group performs a total of 130 hysterectomies and myomectomies; therefore, we anticipate 110 patients will be enrolled in this study during a three year timeframe.

Study-Wide Recruitment Methods

Potential subjects will be patients of The Advanced Gynecologic Surgery Institute. They will be recruited pre-operatively in the office if they are scheduled to have a laparoscopic or robotic- assisted hysterectomy or myomectomy for symptomatic uterine fibroids at ALGH. The purpose, details, and consent for the study will be performed at that time. The study will then be re- discussed with the patients during the surgical consent process.

Patients currently sign a consent form for morcellation per Advocate Health Care guidelines

(Attachment A). They also sign a separate consent for morcellation in a bag specifically developed by The Advanced Gynecologic Surgery Institute (Attachment B). The alternative provided in this consent is to convert to laparotomy. The subjects will sign the existing consents as well as the research consent to participate in the study.

Study Timelines

- The duration of an individual subject’s participation in the study is only the time of their planned surgical hospitalization and their participation in the follow up pain assessments.
- The duration anticipated to enroll all study subjects is approximately one year.
- The estimated date for the investigators to complete this study is Fall 2016 / Spring 2017.

[figure not shown]
Study Endpoints

Primary endpoint: Leakage of egg albumin from the EcoSac bags after isolated bag morcellation or apparent leakage of specimen from the EcoSac bags during isolated bag morcellation.

Secondary endpoints:

- Intra-operative Complications (yes or no)
 - If yes to complications, please specify
- Post-operative Complications (yes or no)
 - If yes to complications, please specify
- Length of stay (hours)
- Admission (yes or no)
- Re-admission (yes or no)
 - If YES, yes to re-admission, specify reason_____
- Morcellation time (minutes) – from insertion of bag to removal of bag
- Technical issues with the use of the bag (yes or no)
- Conversion to open procedure (yes or no)
- Smooth muscle cell clusters in cytologic washings (yes or no)
- Post operative pain (Visual Analog Scale pain scale) (Figure 1)
 - Assessment times: immediate post-operative period (in the recovery room); 1 week post operatively; 2 weeks post operatively, and 4-6 weeks post operatively

Figure 1: Visual Analog Scale - Pain Scale

Other data to be collected include:

- Age
- Race
- Socioeconomic status (including educational level and annual household income)
- Weight
- Height
- Body Mass Index (BMI) (calculated)
- Specimen weight (grams)

Procedures Involved

The study will be a single center, prospective, observational of the EcoSac 400 ECO T. Originally patients were going to be assigned to one of two arms to receive EcoSac 230 (Group 1) or EcoSac 400 ECO-T (Group 2). No random assignment method was to be utilized. Instead, the decision would have been at the surgeon's discretion. Due to improved visualization with the EcoSac 400 ECO T, and the fact that a smaller incision is needed, no patients were enrolled to the EcoSac 230 arm. Due to the fact that the EcoSac 400 ECO T was felt to be a safer procedure, the protocol now only included the EcoSac 400 ECO T.

Patients will be recruited during their pre-operative consent process. All patients will undergo a pre-operative history and physical exam, have an up to date documented pap smear within the last year, and undergo a saline-infused sonohysterogram and endometrial biopsy. Any patient with a fibroid that appears suspicious on ultrasound evaluation will be sent for magnetic resonance imaging (MRI) of their pelvis to further evaluate the fibroid.

All patients undergoing potential morcellation of a fibroid uterus currently sign a consent pre-operatively allowing this process. They will also be consented for morcellation specifically in a specimen bag.

The final evaluation and potential exclusion from the study will occur in the operating room. It will be based on the factors listed above. The alternative to morcellation is converting to laparotomy.

EcoSac 400 ECO-T (EMP 400 ECO-T)

Those patients consented and considered candidates for morcellation with the EcoSac 400 ECO-T will undergo their laparoscopic hysterectomy or myomectomy in the standard technique. A 12 mm umbilical trocar will be used as well as two to three lateral 5 mm trocars under standard technique. After removal of the uterus and/or fibroids, reconstruction of the uterus, and any additional necessary procedure and control of any bleeding, the morcellation portion of the procedure will take place.

The Espiner EcoSac 400 ECO-T will be inserted through the umbilical trocar with a blunt grasper under direct visualization, with the laparoscope placed through a lateral trocar. Once inside the abdomen, the specimen will be placed inside the bag. The accessory sleeve will be grasped through the right lateral 5 mm trocar and is pulled up through the abdominal wall until the entire sleeve is out and the opening to the sleeve is flush with the inside of the abdominal wall. The same 5 mm (non-bladed) trocar is then replaced back into the abdomen through the sleeve so that it is entering into the bag. The string to close the bag will be pulled and the bag will be brought up through the umbilical incision after the trocar is removed while simultaneously providing tension on the right lateral arm to prevent slippage. The insufflation will be hooked up to the right lateral trocar and CO₂ gas will be insufflated into the bag to a pressure of 25 mmHg. Simultaneously, existing gas will be removed from the abdomen. This higher insufflation is necessary to obtain the maximum distension of the bag. Because the insufflation is going directly into the bag and not into the abdominal cavity, the effect of the higher pressure does not cause any increased harm to the intra-abdominal organs. The laparoscope will be placed through the right lateral trocar. Under direct visualization inside the bag, the umbilical incision (where the 12 mm trocar was previously removed) will be dilated to 15 mm. The Storz Rotocut G1 Morcellator will be inserted directly through the umbilical incision and morcellation will proceed as normal. When the EcoSac 400 ECO-T is completely insufflated, it will distend to the sides of the abdominal cavity. The Storz Rotocut G1 Morcellator does not reach the end of this distended bag. Furthermore, the morcellator is placed under direct visualization, assuring no damage to the bag. Once morcellation is complete, all small pieces of tissue will be grasped with a spoon and removed. The inside of the bag will then

be irrigated allowing for removal of any small pieces from the sidewalls of the bag.

After careful inspection to ensure all small pieces are removed, one hundred milliliters of normal saline will be used to gather washings of the inside of the bag. We will perform a “washing” of the inside of the bag that pathology will evaluate for any retained fibroid pieces or cells. After performing the morcellation and removing the bag, we will place an albumin solution with blue dye inside of the bag to assess for any areas of leakage.

This specimen will be sent for cytologic evaluation to evaluate for any smooth muscle cell clusters that may represent pieces of fibroid tissue remaining in the bag prior to removal of the bag. We anticipate cytology to see inflammatory cells, reactive mesothelial cells, and rare red blood cells; but anticipate no smooth muscle cell clusters as we anticipate we will be able to remove all of the fibroid particles and pieces. The patient information will be sent via hospital secured email to the pathology department in order to waive the cytology fee. Although all small pieces will be removed with removal of the intact bag, this will give assurance to the surgeon that all of the pieces can be seen within the bag and therefore can be completely removed.

The CO₂ gas will then be removed from the bag. The right lateral trocar will be removed and the accessory sleeve will be tightly tied off at the most distal end of the sleeve. The entire bag will then be removed from the umbilical incision, pulling the accessory sleeve back through the right lateral incision and out the umbilical incision in the process. The right lateral and umbilical trocars will then be replaced and insufflation will be attached per standard protocol allowing insufflation of abdomen again to a pressure of 15mmHg. Any further portions of the procedure will be completed as needed.

The integrity of the bag will be inspected. Once the bag is removed from the abdomen, it will be taken out of the operating room to the frozen section room. Five hundred milliliters of egg albumin (from egg whites) combined with 0.5 milliliters of methylene blue will be placed into the bag to assess for any leakage. The bag will be insufflated to a pressure of 25mmHg in a box trainer. A positive result will be documented if the egg albumin solution is present on the outside of the bag or dripping from any location. In current testing with Espiner Medical Ltd., egg albumin has been shown to not leak through the EcoSac 400 ECO-T (EMP 400 ECO-T) (Attachment C). The size of egg albumin is approximately 5.5 nm with a gram molecular weight (GMW) of 45,000. Although a hydrogen atom (0.1 nm, GMW 1), water (0.2 nm, GMW 18), and DNA (2 nm) are smaller than egg albumin, viruses and cancer cells are much larger (24-200 nm and 10,000-30,000 nm, respectively) (Attachment D).

Therefore, if egg albumin is unable to leak from the bag despite insufflation, fibroid cells or potentially cancerous cells will also be unable to leak from the bag.

The bag will then be disposed of in the normal post-operative manner in biohazard disposal bags.

Pain will be assessed per routine measures using the VAS pain scale in the post-anesthesia care unit. Patients will then receive a follow up phone call by a member of the research team to assess pain using the same VAS pain scale at 1 week post operatively and 2 weeks post operatively. The patient will have a final pain assessment at their post-operative office visit at AGSI 4-6 weeks post operatively.

The Espiner Medical Ltd. EcoSac 400 ECO-T (product number EMP400ECO-T) is an investigational device created to facilitate contained power morcellation. The bag is

made of Espiner Medical Ltd.'s unique Supramide66™ fabric, which is Polyurethane coated “ripstop” nylon fabric. According to Espiner Medical Ltd., the strong ripstop nylon material prevents the bag from bursting or rupturing. The bag will be removed in its entirety after morcellation and no device will be left in the abdomen. The morcellation will only be completed if adequate insufflation of the bag is obtained leading to appropriate visualization.

See attached for specifications of this device (Attachments E-K).

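### As written, the primary endpoint can score a leaking bag as intact: the bench test need not wet every surface, and specimen leakage has no criterion

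*Combined protocol and SAP*

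**What the plan says.** **Endpoint.** Study Endpoints makes the primary endpoint a composite: albumin leakage in a test after morcellation, or "apparent leakage of specimen from the EcoSac bags during isolated bag morcellation". The second component is given no criterion, observer, time point or method. Objectives sets the hypothesis as no leakage and the goal as proof of bag integrity.

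**Bench test (Procedures Involved, end of the EcoSac 400 ECO-T description).** "Five hundred milliliters of egg albumin (from egg whites) combined with 0.5 milliliters of methylene blue will be placed into the bag". The bag is then insufflated to 25 mmHg in a box trainer. The result is positive if the solution is seen on the bag's outer surface or dripping. Turning, contact time and coverage of walls, seams and sleeve are not mentioned. The same paragraph says "The integrity of the bag will be inspected" but gives no method and no link to the endpoint. Table 2 lists the bag volume as 4200 mL.

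**At surgery (Procedures Involved).** While the bag is inflated, "existing gas will be removed from the abdomen". Then: "The laparoscope will be placed through the right lateral trocar. Under direct visualization inside the bag", after which the incision is dilated and morcellation proceeds. Before bag removal, "one hundred milliliters of normal saline will be used to gather washings of the inside of the bag". After removal the trocars are replaced, "allowing insufflation of abdomen again to a pressure of 15mmHg", and the rest of the operation is finished as required.

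**Analysis.** Results/Statistics gives, as an example of a categorical variable, leiomyoma tissue or cells in washings of the abdomen and pelvis.

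**The concern.** The study hopes to observe no leaks, so every missed leak counts in favour of its hypothesis.

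On the bench, a hole that never comes into contact with the fluid can pass only gas, and gas is not a positive result. Following the written test exactly can therefore classify a leaking bag as intact. The protocol's argument that a bag impermeable to albumin is impermeable to cells applies only to the wall that the albumin touched.

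At surgery, spilled tissue would lie outside the bag, where the described camera position does not look. The re-insufflation after bag removal would allow a look, but none is specified. The washing described samples the inside of the bag, so it shows residue rather than escape. The abdominal and pelvic washings named in Results/Statistics would bear on escape, but no described step collects them.

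The stopping rule in Data Management also uses the albumin leakage rate, so missed leaks would weaken that safeguard too.

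**Working it through.** The plan states no test sensitivity, expected leak rate or precision target, so there is no figure of its own to reproduce.

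**1. Fluid against bag volume.** 500 mL (Procedures Involved) / 4200 mL (Table 2) = 11.9%. In a fully distended bag about 88% of the volume would be gas. This gives the share of volume, not the share of wall wetted.

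**2. What each described step can show**

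| Step | Where it looks | Part of the primary endpoint? |
|---|---|---|
| Laparoscopic view during morcellation | Inside the bag | Not stated; apparent leakage is undefined |
| 100 mL washing | Inside the bag | No; cytology is secondary |
| Re-insufflation to 15 mmHg | Abdomen, but no look for tissue specified | No |
| General inspection of the bag | The bag, method not given | No link stated |
| Albumin test | Outer surface of the bag | Yes, for holes the fluid reaches |
| Abdominal and pelvic washings | Outside the bag, no collection step | No |

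**3. Effect on a zero-leak result (illustrative).** Inputs: n = 110, the stated maximum; 0 leaks recorded; one-sided 95% confidence. The plan reports descriptively, so this bound is ours. Let p be the true leak rate and S the share of leaks that the two components catch together. Assume independent bags and the same S for every leak.

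- Zero recorded: (1 − pS)^110 = 0.05, so pS = 1 − 0.05^(1/110) = 2.69%.
- Hence the upper bound on p is 2.69%/S.

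| S (assumed) | Upper bound on true leak rate |
|---|---|
| 1.0 | 2.7% |
| 0.9 | 3.0% |
| 0.75 | 3.6% |
| 0.5 | 5.4% |

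**4. The same effect seen from the other side.** With a true leak rate of 3%, the chance of recording no leak in 110 is 0.97^110 = 3.5% at S = 1 and (1 − 0.015)^110 = 19% at S = 0.5.

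**The case against.** **Handling may wet the whole bag.** The fluid goes in before insufflation, the box trainer may limit distension, and carrying or filling the bag may spread the fluid. Attachment C, on the manufacturer's albumin testing, was not available and may describe the handling. This stands as a limit on size: if S is 0.9, the bound moves only from 2.7% to 3.0%. It does not remove the point, because the written test does not require the contact.

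**Surgeons would notice a tear.** Morcellation is done under direct vision and only with adequate insufflation. Risks to Subjects describes a response to a tear, so it presumes recognition, and technical issues with the bag are a secondary item. These are real safeguards and will raise S. None is stated as a criterion for the primary endpoint, and none is certain to catch a small hole.

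**This is a feasibility study with descriptive reporting.** True, and it argues against treating the point as fatal. But Objectives still speaks of proving integrity and confirming safety and efficacy.

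**A tempting stronger reading: nobody looks outside the bag.** The documents do not support this. The bench test examines the outer surface, and Results/Statistics names an outside-bag washing. What is missing is a specified look in the abdomen for spilled tissue.

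**Another: only about a fifth of the wall is tested.** A still, fully distended sphere would have 21.5% of its wall wetted (solve 3x² − 2x³ = 500/4200). With no recognition at surgery the bound would then be 2.69%/0.215 = 12.5%. The documents establish neither the shape, the stillness, full distension nor the absence of recognition, so 12.5% is not a finding.

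**Conclusion.** The point holds in a limited form. Followed as written, the primary endpoint can miss a leak: on the bench because fluid contact with every surface is not required, and at surgery because specimen leakage is undefined and no look in the abdomen is specified. Zero recorded leaks would therefore not by themselves show bag integrity. A reader might infer that such a result would be worthless, or that leaks have been missed; the documents support neither.

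The size cannot be determined, because it depends on S and the documents do not give S. Over an assumed S from 1 to 0.5, the bound for 0 of 110 runs from 2.7% to 5.4%. The change should be made because it is cheap and closes a false-negative route that favours the hypothesis.

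**What to change.** 1. **Bench test.** Turn the inflated bag so that all walls, the seams and the sleeve are each under the fluid for a fixed time. The protocol does not say how the mouth is sealed in the box trainer, so record leakage at the test closure itself separately, outside both the endpoint and the leakage rate in the stopping rule.
2. **Specimen leakage.** Count as positive either a tear recognised during morcellation or tissue seen outside the bag. The tear must count by itself, because the irrigation described in Risks to Subjects could clear tissue before any later look. Record a yes/no look before the bag is closed and again at the planned re-insufflation, because the specimen is detached before bagging and tissue predating the bag should not be counted. Apply the bench test to any bag that is replaced.
3. **Pressure.** Record failure to hold 25 mmHg in the bench test as a separate item.
4. **Washings.** Reconcile Procedures Involved with Results/Statistics on which washings are collected.
5. **Reporting.** Give results overall and separately for cases tested before and after the change.

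**Cost.** A protocol modification through IRB and IDE review, some case report form lines, the two recorded looks, and a few minutes per case (assumed; the documents give no figure). Prior Approvals lists initial approval in April 2016 and DSMB reports from December 2016, so cases may already have been done, and discarded bags cannot be retested. Reporting by period costs precision: with an assumed even split, 0 of 55 gives 1 − 0.05^(1/55) = 5.3% at complete detection. That is looser than the overall 2.7%/S unless S is about 0.5 or lower, but it does not depend on an unknown S if the revised procedure detects every leak. This is why both results should be shown.

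### A leak-free bag supports bag integrity only: the primary endpoint and the one described washing cannot detect tissue carried into the abdomen on instruments used inside the bag

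*Combined protocol and SAP*

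**What the plan says.** **Procedures Involved, EcoSac 400 ECO-T, before and during morcellation.** Once the accessory sleeve has been drawn out through the right lateral port, "The same 5 mm (non-bladed) trocar is then replaced back into the abdomen through the sleeve so that it is entering into the bag". The camera follows: "The laparoscope will be placed through the right lateral trocar". The umbilical trocar is out by then: "the umbilical incision (where the 12 mm trocar was previously removed) will be dilated to 15 mm", and the morcellator passes directly through that incision.

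**Same section, after morcellation.** Small pieces are taken out with a spoon, the bag is irrigated and inspected, and 100 mL of saline is used to wash its interior for cytology. Then "The right lateral trocar will be removed and the accessory sleeve will be tightly tied off at the most distal end of the sleeve". The bag leaves through the umbilicus, "pulling the accessory sleeve back through the right lateral incision and out the umbilical incision in the process". The next sentence is "The right lateral and umbilical trocars will then be replaced and insufflation will be attached per standard protocol". The abdomen is re-insufflated, and "Any further portions of the procedure will be completed as needed".

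**Study Endpoints.** The primary endpoint is albumin leakage from the bag afterwards, or visible escape of specimen from the bag during morcellation. A secondary endpoint records smooth muscle cell clusters in washings, without naming the site.

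**RESULTS/STATISTICS.** The example given of a categorical variable is leiomyoma tissue or cells in washings of the abdomen and pelvis after contained morcellation.

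**Objectives.** The hypothesis is that the bag stays intact and does not leak, "confirming the safety and efficacy of the systems".

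**The concern.** The purpose of the bag is to keep morcellated tissue out of the abdomen. The bag wall is one route by which that can fail. An instrument that has been among the fragments and then enters the abdomen is another, and it does not involve the wall. If tissue travelled that way, the bag could be intact, the bench test negative and the case scored a success.

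The leak data are not at stake; they remain valid for what they measure. What is at stake is the step from no leakage to a statement about the system as a whole, which needs every route around the bag to be either measured or set aside by argument. The plan does neither for this route.

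**Working it through.** The plan gives no figure on this point to reproduce, and no power or precision basis for the maximum of 110 patients. The check is mainly a trace of the text.

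**Step 1: what was in the bag.** The right lateral trocar and the laparoscope were, by explicit statement. The 12 mm umbilical trocar was not; it had been removed beforehand. The sentence on re-entry covers both trocars, but only the right lateral one matters here.

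**Step 2: what goes back in.** The right lateral trocar is *replaced*. Where the same section describes entry into the bag, it uses that verb for putting the same trocar back, and says so. At re-entry neither *same* nor *new* appears, and no cleaning or exchange is written. Re-use is the natural reading but is not stated. The laparoscope is not mentioned at this step; its return is implied by any further abdominal work.

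**Step 3: what is sampled.**

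| Measure | Site and timing | Could it register carry-over after bag removal? |
|---|---|---|
| Primary endpoint, visible specimen leak | From the bag, during morcellation | No: earlier in time, and concerns the bag |
| Primary endpoint, albumin test | Bag, on the bench after removal | No: tests the bag wall |
| Cytology as described in Procedures Involved | Bag interior, before removal | No: shows residual tissue in the bag, not transfer |
| Cytology as listed in Study Endpoints | Site not named | Cannot be judged |
| Washings named in RESULTS/STATISTICS | Abdomen and pelvis, after morcellation | Possibly, if taken after re-entry; no collection step is given |

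Table 1 (Schedule of Activities) lists bag testing at surgery and no abdominal or pelvic washing. The last row also conflicts with the third: the same kind of outcome has two different sites.

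**Step 4: what a perfect leak result would show.** Input: n = 110 (Study-Wide Number of Subjects), assuming full enrolment and 0 leaks. The exact upper bound on the leak rate is 1 − α^(1/n).

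- One-sided 95%: 1 − 0.05^(1/110) = 0.0269, or 2.7%.
- Two-sided 95%: 1 − 0.025^(1/110) = 0.0330, or 3.3%.

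Both are bounds on bag leakage. Carry-over does not enter the primary outcome, so the result gives no bound on it.

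**Step 5: illustration with assumed carry-over rates.** The documents give none. For a rate c, with no bag leaks, the expected number of cases is 110c and the chance of at least one is 1 − (1 − c)^110.

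| Assumed c | Expected cases in 110 | Chance of at least one | Leaks recorded |
|---|---|---|---|
| 1% | 1.1 | 67% | 0 |
| 5% | 5.5 | 99.6% | 0 |
| 10% | 11 | over 99.9% | 0 |

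The leak count is the same in every row, so it cannot distinguish these situations.

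**The case against.** The strongest reply has four parts.

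*The plan already names a variable that could sample the abdomen.* This stands in part. A reader might infer that nothing in the plan could detect carry-over; the washings in RESULTS/STATISTICS rule out putting it so absolutely. But the text available for review does not say when or how they are taken, and Procedures Involved describes a washing at a different site.

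*Re-entry of contaminated instruments is inferred.* This stands. A reader might conclude that the trocar and laparoscope used in the bag go back in unchanged in every case, up to 110 of 110. The documents do not say so: the wording leaves exchange open and does not mention the laparoscope. The figure 110 is only a ceiling on exposure, not a contamination rate.

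*The procedure reduces the risk.* This also stands in part. Pieces are removed, the bag is irrigated and inspected, and the cytology is an indirect check on what is left in it shortly before the trocar comes out. None of this examines instrument surfaces. The sleeve might also be suspected, but it is tied off before being drawn back, and the documents do not support treating it as a comparable route.

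*The claim is already limited.* This is mostly right. The stated goal in Objectives is bag integrity, which the primary endpoint matches, and the argument from albumin size in Procedures Involved concludes only about leakage from the bag. The overreach is confined to the closing clause of the hypothesis.

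**Conclusion.** The concern holds in a limited form. Neither the primary endpoint nor the only washing with a described collection step can detect tissue carried into the abdomen on an instrument that was inside the bag. A leak-free series would support bag integrity, but the system-level conclusion in the hypothesis would not follow from it.

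The size cannot be given. Whether carry-over occurs, and how often, is not determinable from the documents, and the rates in the illustration are assumptions. The conclusion does not depend on them, nor on proving that the same trocar is re-used: it is enough that the text leaves re-use open and that no defined sample covers the abdomen after re-entry. It does assume that no collection step for abdominal and pelvic washings exists in the part of the document that was not available for review.

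The point is worth correcting before results are reported, because it changes what the trial may conclude.

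**What to change.** 1. **Objectives.** Limit the conclusion drawn from the primary endpoint to bag integrity, and state that carry-over on instruments is not tested. The albumin argument in Procedures Involved needs no edit.
2. **Washings.** Reconcile Study Endpoints, Procedures Involved and RESULTS/STATISTICS on the site and timing of the washings. Make no system-level containment claim unless the abdominal and pelvic washings are defined and actually collected.
3. **Re-entry step.** The surgical team should reconcile the word *replaced* with the containment purpose, so that the text says what happens to instruments used in the bag. The technique is theirs to choose.
4. **Optional.** Record for each case whether an instrument used in the bag re-entered the abdomen unchanged, and report the count beside the leak result. This measures exposure; it cannot show whether tissue was carried.

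The cost of items 1 to 3 is wording, plus collection and cytology work if the abdominal and pelvic washings are kept. Item 4 adds one case-record item. The downside is a narrower containment claim.
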